7.3 Duration of Participation

Describe the duration of an individual subject's participation in the study.

Screening (1 Visit)	less than 1.5 hour
---------------------	--------------------

MD Experiments (2 Visits)	5 hours
---------------------------	---------

Total: ~11.5 Hours

7.4 Test Article(s) (Study Drug(s) and/or Study Device(s))

7.4.1 Description

Provide a brief description of all test articles (drugs (including any foods and dietary supplements), devices and/or biologics used in the research including the purpose of their use and their approval status with the Food and Drug Administration (FDA). Include information about the form of the drug product (e.g., tablets, capsules, liquid).

Investigative Substances: Microdialysis

Acetylcholine ACh Form: solid

Role in Current Study: The local perfusion of endothelial agonist, acetylcholine, specifically examines the attenuated endothelium-dependent vasodilation associated with endometriosis.

Atorvastatin Form: solid

Role in Current Study: Atorvastatin is a LOX inhibitor.

Lactated Ringer's Ringer's Form: Liquid

Role in current study: Lactated Ringer's acts as the vehicle for the other research substances and as a flush.

LNAME NG-nitro-L-arginine methyl ester Form: solid

Role in current study: A nitric oxide synthase inhibitor. L-NAME is an analog to the amino acid, L-arginine. L-NAME is a non-specific inhibitor for nitric oxide synthases, thereby inhibiting the production of nitric oxide that causes vasodilation.

Polyinsinoic Acid Poly I:C Form: solid

Role in Current Study: Polyinosinic Acid is a LOX-1 receptor antagonist.

Sodium Nitroprusside SNP Form: solid

Role in Current Study: SNP, acting as an NO donor, dilates blood vessels maximally thereby, combined with local heating, achieving maximal skin blood flow (SkBF). Maximal SkBF is a reference point for other measures of skin blood flow.

Investigative Substances: Oral

Atorvastatin Brand name: Lipitor Form: tablet

Role in Current Study: Atorvastatin acts as a systemic LOX inhibitor.

7.4.2 Treatment Regimen

Describe dose, route of administration and treatment duration. Include information about dose adjustments.

Investigative Substances: Microdialysis

The following is a table of the research agents used with intradermal microdialysis. Based upon research literature, we use 14% for calculating maximum delivery of the research agents for all IND applications for our MD studies.

Research Agent	14% delivery (mg)
ACh	0.025
Atorvastatin	0.00061
L-NAME	0.091
Poly I:C	0.1
SNP	0.023

Investigative Substances: Oral

Atorvastatin 10 mg/day for 6-9 days

7.4.3 Method for Assigning Subject to Treatment Groups

Describe the randomization process and how the associated treatment assignment will be made.

Not Applicable

7.4.4 Subject Compliance Monitoring

Insert the procedures for monitoring subject compliance.

We note remaining atorvastatin tablets when subject returns for post-treatment experiment.

7.4.5 Blinding of the Test Article

Describe how the test article is blinded.

Not Applicable

7.4.6 Receiving, Storage, Dispensing and Return

7.4.6.1 Receipt of Test Article

Describe how the test article will be obtained and from what source. Describe how the study test article will be packaged along with amounts (e.g., number of tablets/capsules or volume of liquid) and labeling. If drug kits are used, describe all the contents of the kit and associated labeling.

See uploaded Physician Oversight SOP.

Investigative Substances: Microdialysis

Detailed records are kept in laboratory log books. The containers of the substances are dated upon receipt and when opened.

Investigative Substance	Source(s)
ACh	USP
Atorvastatin	USP
L-NAME	EMD, Tocris
Lactated Ringer's	McKesson, Moore Medical
Poly I:C	Invivogen
SNP	USP

From uploaded Physician Oversight SOP:

The investigative agents are purchased by the lab members from reputable sources as indicated in the IRB and the FDA IND applications and in accordance with the standards and guidelines imposed by the FDA.

A license from the CRC physician, the nurse manager, or the overseeing physician is filed with vendors (e.g. VWR, Owens and Minor) requiring the documentation for the purchase of some investigative agents (e.g. Lactated Ringer's).

The investigative agents are shipped to the Noll Lab or picked up from the pharmacy by lab personnel.

Copies of the prescriptions and orders are maintained in the laboratory's files.

Investigative Substances: Oral

A prescription, written by a study physician, for the Atorvastatin (10mg/tablet, 9 tablets) is filled by the Boalsburg Apothecary for each study participant. Detailed records are kept in laboratory log books and in individual subjects' charts. All medications will be double-checked by two people to ensure correctness.

Atorvastatin (Lipitor) Boalsburg Apothecary

From uploaded Physician Oversight SOP:

Some of the investigative agents are prescription drugs... The lab personnel obtain prescriptions from a CRC physician, the research nurse manager, or the overseeing physician for the investigative agents that are prescription drugs and forward the prescriptions to the pharmacy.... The investigative agents are shipped to the Noll Lab or picked up by lab personnel.

A license from the CRC physician, the research nurse manager, or the overseeing physician is filed with reputable vendors requiring the documentation for the purchase of some investigative agents.

Copies of the prescriptions and orders are maintained in the laboratory's files.

7.4.6.2 Storage

Describe the plans to store, handle the test article so they will be used only on subjects and only by authorized investigators. Describe storage temperature requirements and how temperature will be monitored and recorded.

Investigative Substances: Microdialysis

The investigational substances are stored under environmental conditions according to manufacturers' instructions in cabinets, refrigerators, or freezers located in Room 229 or 224A Noll Laboratory. The room is locked when unoccupied. Each location has a thermometer. The temperatures are recorded daily during weekdays. The temperature of the room is also monitored by the Central Control System of the Environmental Systems at PSU.

Investigative Substances: Oral

We store the drugs in a locked cabinet in Room 229 under environmental conditions according to manufacturers' instructions. The room is locked when unoccupied. The location has a thermometer. The temperatures are recorded daily during weekdays. The temperature of the room is also monitored by the Central Control System of the Environmental Systems at PSU.

7.4.6.3 Preparation and Dispensing

Describe how the test article will be assigned to each subject and dispensed. Describe the steps necessary to prepare the test article. Include where the test article preparation will be done and by whom. Fully describe how the study treatment is to be administered and by whom.

Investigative Substances: Microdialysis

None of the microdialysis drugs are dispensed to the participant; rather we use them in the experiment, as outlined in the Standard Operating Procedures (Phys Ovrsht SOP). The physician providing oversight approves the laboratory standard operating procedure for the obtainment, preparation, and administration of all investigational agents for MD and other procedures in experiments.

The following procedures have been examined and approved by the FDA.

Trained lab personnel prepare the perfusates in accordance with the procedure described in the IRB and FDA IND applications. When mixing the perfusates, the experienced technician washes the hands, wears protection (e.g. gloves, lab coat), and uses glassware that has been washed with cleaner (designed for use with healthcare instruments, pharmaceutical process equipment, tissue culture apparatus, etc.), and rinsed multiple times in tap and then doubly- distilled water and air-dried. Most of the investigational agents are obtained in ultra-pure solid form. The solid investigational agents are weighed on a microbalance and then mixed with sterile pharmaceutical-grade Lactated Ringer's solution to the desired concentration. The solution is drawn into the syringe through a 0.2 µm filter. Prior to injecting a solution into or withdrawing solution from a sterile container through a sterile hypodermic needle, the stopper of the sterile container is cleaned thoroughly with alcohol. Most perfusates are used within minutes or hours after preparation. Stock solutions are made for some investigational agents. The stock solutions are drawn into sterile 1-cc syringes through 0.2 µm filters for storage. The sterile stock solutions are labeled accordingly (e.g. content, date), and protected from light. Stock solutions are not used beyond 1 week (refrigerated) and 6 months (frozen) after mixing. Stock solutions are diluted with

sterile Lactated Ringer's when preparing the perfusate. The final dilutions of the perfusates are drawn into sterile syringes through 0.2 µm filters within minutes or hours of their use in the experiment. The protocol that includes the administration of the investigative substances has been examined and approved by the FDA. The administration of the investigative substances is performed by the trained and approved lab personnel as described in the protocol included in the IRB and FDA IND applications. The overseeing physician has observed and approved the microdialysis technique as performed by [name]. The lab personnel performing microdialysis have been trained and approved to perform the technique by [name], approved by the overseeing physician, and approved by the IRB. Letters of approval from the overseeing physician for each member of the lab who performs microdialysis in the research project have been submitted to the IRB.

Investigative Substances: Oral

The Boalsburg Apothecary places the pills into bottles labeled with the subject ID number, strength (mg), dosing instructions, date, etc. Each bottle contains the number of pills as prescribed by a study physician. All medications will be double-checked by two people to ensure correctness. The research nurse gives the bottle of pills to the subject along with handouts that contain detailed information and dosing instructions pertinent to their assigned drug. Detailed records are kept in laboratory log books and in individual subjects' charts.

7.4.6.4 Return or Destruction of the Test Article

Describe the procedures for final reconciliation of the test article supply at the end of the study and whether the test article is to be shipped back to a source or destroyed on site.

Subjects are required to return unused pills to investigators. The pills are disposed of in accordance with policies of the Penn State's Environmental Health and Safety Department at University Park.

7.4.6.5 Prior and Concomitant Therapy

Describe what prior and/or concomitant medical therapy will be collected. Describe which concomitant medicines/therapies are permitted during the study. Describe which concomitant medicines are not permitted during the study.

Subjects are excluded if they are currently taking chronic medications that may affect vascular function or are contraindicated for the atorvastatin pharmacotherapy. Medications that are not specifically mentioned in exclusion criteria may be excluded on a case by case basis upon review by the research clinicians or PI.

8.0 Subject Numbers and Statistical Plan

8.1 Number of Subjects

Indicate the total number of subjects to be accrued.

If applicable, distinguish between the number of subjects who are expected to be enrolled and screened, and the number of subjects needed to complete the research procedures (i.e., numbers of subjects excluding screen failures.)

Anticipated number of subjects to be screened: 10

Needed to complete: 6

The pilot experiments will enable the determination of the number of subjects needed for completion of the study. A future modification to this study will update number of subjects.

8.2 Sample size determination

If applicable, provide a justification of the sample size outlined in section 8.1 – to include reflections on, or calculations of, the power of the study.

The pilot experiments will enable the determination the number of subjects needed for completion of the study. A future modification to this study will add that number of subjects.

8.3 Statistical methods

Describe the statistical methods (or non-statistical methods of analysis) that will be employed.

Descriptive statistics will be calculated and the variance will be noted for a full power analysis. If appropriate, three-way repeated measures ANOVA (ANCOVAs) will be performed to examine group differences (healthy control vs. endometriosis) or systemic treatment differences (pre-treatment vs. post-treatment), and local microdialysis treatment differences across the doses of pharmacological stimuli with the primary outcome variable of cutaneous vascular conductance. Appropriate post-hoc analyses with corrections for multiple comparisons will be performed when main effects are identified, in all cases including potential confounding variables as covariates.

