1.2 Primary Study Endpoints

State the primary endpoints to be measured in the study. Clinical trials typically have a primary objective or endpoint. Additional objectives and endpoints are secondary. The endpoints (or outcomes), determined for each study subject, are the quantitative measurements required by the objectives.

Measuring the selected endpoints is the goal of a trial (examples: response rate and survival).

Skin blood flow (cutaneous vascular conductance)

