2.3 Study Rationale

Provide the scientific rationale for the research.

Cardiovascular disease (CVD) is the leading cause of death in women. Endometriosis is associated with higher risk of hypercholesterolemia and hypertension⁸. Epidemiologic data demonstrate a clear association between endometriosis, reproductive risk factors, inflammation and cardiovascular (CV) risk^{5,8-11}. Our scientific premise is that in women with endometriosis, elevated cardiovascular disease risk is the result of endothelial dysfunction and chronic systemic inflammation through LOX-1 receptor activation. We will explore microRNA (miRNA) activation of LOX-1 receptor mechanisms as one factor mediating the elevated risk of CVD in endometriosis.

Lipitor is a commonly used statin that has pleotropic effects. One of those is to inhibit the LOX receptor and decrease the microRNAs that stimulate the LOX receptor. We will test this on an acute (receptor activation level) with microdialysis and on a systemic level. Additionally, statins have been proposed and tested in animals to decrease the endometriosis associated inflammatory and microRNAs we hypothesize to be driving the accelerated CVD risk. The short term oral statin will help us delineate this putative effect/mechanism."

The current application comprises pilot experiments designed to yield data for the development of the final protocol. Modifications (e.g. doses of some of the investigational substances, number of subjects needed to complete study, etc.) to this protocol will be made in the future based on the results of the pilot experiments.

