7.2.2 EXAMPLE: Visit 2 or Day 2 or Post-test, etc. (format accordingly)

Provide a description as defined above and format accordingly.

Note: Subjects perform a pre- and post-statin therapy experiment.

1. Preparation for experiments
 - a. We give printed and verbal instructions outlining what the subjects need to do before they come to the lab.
 - b. Subjects continue with their normal diet except:
 - i. They refrain from consuming alcohol and caffeine (ex. coffee, tea, Coca Cola, chocolate) for 12 hours before the experiment.
 - c. On the day of the experiment,
 - i. Subjects refrain from activity that causes them to exert themselves more than a leisurely walk.
 - ii. We measure HR, BP, and oral temperature. Women who are not postmenopausal undergo a urine pregnancy test if they have not been tested within 2 weeks.
 - iii. The nurse draws 10 ml blood for analysis of relevant substances of interest such as miRNA, soluble LOX receptor, OxLDL, IL6, IL17, and TNF α .
 - iv. Microdialysis probe insertion: The subject washes the ventral forearm with antimicrobial soap. We place a tight band around the arm so we can visualize veins. For each MD site, we make pairs of pen-marks on the arm 2.5 cm (1 inch) apart and away from veins. We remove the tight band. The MD tubing enters and exits the skin at the marks. We clean the arm with povidone iodine and alcohol. We place an ice bag on the arm for 5 minutes to numb the skin. Then we insert a thin needle into the skin at each entry mark. The needle's tip travels between the layers of skin for 2.5 cm (1 inch) and leaves the skin at the matching exit mark. We thread the MD tubing through the needle. Next, we withdraw the needle leaving the tubing in the skin. Any redness of the skin subsides in about 60 – 120 minutes.
 - v. We initiate lactated Ringer's perfusion in all MD probes at 2 μ l/min.
 - vi. We attach 3 ECG leads to measure heart rate, and place a cuff on the upper arm sans the MD probes to measure blood pressure. We place a local skin heater and laser Doppler probe over each MD site. We measure heart rate, local temperature, and skin blood flow (SkBF) throughout the MD experiments. We also measure blood pressure every 5-7 minutes (brachial osculation and/or critical care monitor).
2. MD Experiment – Pre-Statin Therapy

a. Acetylcholine (ACh) Dose Response

We prepare 5 MD sites: Probe 1. Lactated Ringer's only (control)

Probe 2. Lactated Ringer's + LNAME

Probe 3. Lactated Ringer's + Poly I:C

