Probe 4. Lactated Ringer's + atorvastatin

Probe 5. Lactated Ringer's + (LNAME + Poly I:C) or (LNAME + atorvastatin)*

*Note: Pilot experiments lead to development of the final protocol. Two treatments are explored at MD Probe 5 during pilot experiments. Pilot experiments also determine final doses of investigational agents.

We clamp the temperatures of the local heaters at 34°C (93°F). We add Poly I:C or atorvastatin to probes 3, 4, and 5 as indicated above. After 30 minutes, we add LNAME to Probes 2 and 5. Twenty minutes later, we record a 10-minute baseline. After the baseline, we add the first concentration of ACh to the perfusate at each probe. Each site receives 6 increasing concentrations of ACh (10⁻¹⁰M to 10⁻¹M) each concentration is perfused for 5 minutes. As SkBF stabilizes with the addition of each concentration of ACh, we proceed to the next concentration. After the last concentration of ACh, we switch perfusates at all sites to Ringer's only for about 30 minutes while increasing the local temperature to 43°C. We add SNP to lactated Ringer's for 10 minutes at each site. Heating and SNP perfusion causes maximum vasodilation.

- b. Then the experiment is over, and we remove the MD tubing from the skin and place sterile bandages over the sites. If the subject desires, we can also place a bag of ice on the site for 10 minutes to reduce any bruising that may occur. We measure blood pressure and heart rate before the subject departs.
3. Subjects take 10 mg/day atorvastatin for 6-9 days. Women who are not postmenopausal undergo a urine pregnancy test before beginning the atorvastatin.
4. Venous blood may be drawn for Chem 24 analysis if a subject experiences side effects from the statin therapy (e.g. dark urine, muscle myalgia).
5. MD Experiment – Post-Statin Therapy
 - a. The subjects return to the lab to repeat the MD experiment within days 6-9 of atorvastatin therapy.
 - b. On the morning of the experiment, the subjects take their final dose of atorvastatin.
 - c. All other preparation and procedures are the same as described for the Pre-statin Therapy MD Experiment.

Equipment:

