Laser Doppler Flowmetry: The Laser Doppler Flowmeter (Moor Instruments, Inc.) non-invasively provides a qualitative measure of skin blood flow to a depth of about 1 mm in the skin using a weak laser light. This measure is a dimensionless value called "flux" that reflects the speed and number of blood cells moving through the microvasculature in an area of skin. The flowmeter continuously measures skin blood flow using a fiber optic probe that fits into holders taped to the skin. Approved by the FDA

Blood Pressure, ECG (Heart rate): The critical care monitor measures blood pressure via a cuff inflated every 5-7 minutes on the upper arm and heart rate via 3-lead ECG probes taped to the skin of the chest. Approved by the FDA

12-lead ECG: The critical care monitor measures standard 12-lead ECG during screening via electrodes taped to the skin. Approved by the FDA

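### Does naming the primary outcome only as cutaneous vascular conductance, with no scale and no rule for placing agents on the forearm, require a change to this pilot plan?

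*Combined protocol and SAP*

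**What the plan says.** Section 1.2 lists one primary endpoint: skin blood flow, with cutaneous vascular conductance (CVC) in parentheses. Section 8.3 plans repeated-measures ANOVA, where appropriate, "with the primary outcome variable of cutaneous vascular conductance". Neither section gives a pressure denominator, a unit or a scale.

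Other sections bear on the scale. The equipment notes in Section 7.2.2 describe laser Doppler flux as a dimensionless, qualitative signal. After the last acetylcholine dose, every site is warmed to 43°C for about 30 minutes and then receives SNP for 10 minutes; the protocol explains that "Heating and SNP perfusion causes maximum vasodilation". Section 7.4.1 gives the purpose: "Maximal SkBF is a reference point for other measures of skin blood flow".

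On placement, Section 7.2.2 ties agents to probe numbers 1 to 5 and says "For each MD site, we make pairs of pen-marks on the arm 2.5 cm (1 inch) apart and away from veins". It does not link probe numbers to positions on the forearm. The post-statin visit otherwise follows the pre-statin procedures.

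On purpose, Section 2.3 describes "pilot experiments designed to yield data for the development of the final protocol". Section 8.1 needs six women to complete, Sections 8.1 and 8.2 leave the final number to a future modification, and Section 8.3 says "the variance will be noted for a full power analysis".

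**The concern.** Flux has arbitrary units, and its level depends on the skin and probe at each site. Comparisons are planned between women, between five sites and between two visits with newly inserted probes. If absolute CVC were analysed, differences in site gain would enter all three. If CVC is divided by the same site's maximum, the gain cancels, but error in measuring the maximum enters instead.

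The two scales can also answer different questions. Suppose both groups respond at 60% of maximum, with maxima of 2.0 and 1.6 flux units per mmHg (assumed). Absolute CVC is then 0.60 × 2.0 = 1.20 against 0.60 × 1.6 = 0.96, a 20% deficit, while the percentage scale shows 60 against 60.

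Three things seem to be at stake: the variance handed to the power analysis, freedom to choose the primary scale after seeing the data, and possible confounding of local agents with forearm position.

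**Working it through.** **1. Is the scale really open?** The sections side by side:
- Section 1.2 names skin blood flow, as CVC, as the endpoint.
- Section 7.2.2 obtains a maximum at every site in both visits, at a cost of about 30 + 10 = 40 minutes each time.
- Section 7.4.1 says the maximum is the reference for the other blood-flow measures.

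Read together, these point to CVC relative to the site maximum. What is missing is a confirming sentence in Sections 1.2 and 8.3.

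**2. Is information lost if the scale is not named now?** CVC on either scale needs flux, pressure and, for the percentage scale, the maximum. Section 7.2.2 collects flux throughout, pressure every 5–7 minutes, and the maximum at each site. Both variances can be computed from the same records.

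**3. Do the documents show that one scale is better?** They give no SDs. Assume a mean response of 60% of maximum, SD 12 between women and 6 between sites, gain CV *g* of 10–40%, and error CV *e* in the maximum of 5–15%.

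Between women, c = (12² + 6²)/60² = 180/3600 = 0.05, and

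ratio (absolute / % maximum) = [(1 + c)(1 + g²) − 1] / [(1 + c)(1 + e²) − 1].

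The numerators are 0.0605, 0.0920, 0.1445 and 0.2180 for g = 10, 20, 30 and 40%. The denominators are 0.0526 for e = 5% and 0.0736 for e = 15%.

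| Gain CV | 10% | 20% | 30% | 40% |
|---|---|---|---|---|
| e = 5% | 1.15 | 1.75 | 2.75 | 4.14 |
| e = 15% | 0.82 | 1.25 | 1.96 | 2.96 |

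The ratio equals 1 when g = e.

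For two sites in the same woman, remove the shared part, 12²/60² = 0.04. With independent gains and e = 5%, the ratio is (numerator − 0.04)/(0.0526 − 0.04), giving 1.6, 4.1, 8.3 and 14. With e = 15% and lognormal gains correlated 0.5 within a woman, it is [1.05(1 + g²) − 1.04√(1 + g²)]/(0.0736 − 0.04), giving about 0.5, 0.9, 1.7 and 2.9.

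Across these inputs the ratio runs from about 0.5 to 14.

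**4. Does a sample-size comparison settle it?** For two groups, 80% power, two-sided 5% and a 25% relative difference, n per group = 2(1.960 + 0.842)² CV²/0.25² ≈ 251 CV². The percentage scale needs 14–19 per group (CV² 0.0526–0.0736), and absolute CVC needs 16–55 (CV² 0.0605–0.2180).

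This assumes the same 25% effect on both scales. If the impaired group's maximum is also 10% or 20% lower, the absolute effect is 1 − 0.75 × 0.90 = 32.5% or 1 − 0.75 × 0.80 = 40%. Absolute CVC then needs 9/14/22/33 or 6/10/15/22 per group at the four gain CVs, so the ranking can reverse. The formula is also not the repeated-measures model of Section 8.3.

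**5. Placement.** Five agents on five positions have 5! = 120 orders. Neither 6 women nor 6 × 2 = 12 sessions is a multiple of 5, so exact position balance is impossible at this size. Placement that varies without pattern adds noise; bias needs agents consistently tied to positions, and nothing in the documents says they are. Reusing positions at the second visit has a cost: that visit falls on days 6–9 of therapy, and Section 11.0 says bruising from probe insertion is common, so the skin may not be comparable.

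**6. Pressure timing.** With strict 5-minute doses and readings every k minutes (k from 5 to 7), 6 − 30/k of the six doses lack a reading on average: 0 at k = 5, 1.0 at k = 6, 1.7 at k = 7. Section 7.2.2 also ties dose steps to stabilising flow, so strict steps are an assumption, and no effect on any result is shown.

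**The case for a change.** The strongest argument for a change is that the pilot's statistical product is a variance, and a variance has no meaning without a scale. A line in a drug description is not an endpoint definition, and it does not rule out analysing absolute CVC. With six completers and no declared scale, an investigator could prefer whichever version looks better. The remedy would cost a sentence or two and a short placement list.

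Part of this stands. The confirming sentence is absent, the two scales can disagree, and naming the scale in advance is better practice.

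It does not carry the point further. The variance can be reported on both scales from data already planned, so the later power analysis loses nothing. Choosing a scale after the fact has limited weight where the certain output is descriptive and ANOVA is conditional on being appropriate. The further step, prescribing percentage of maximum, fixed positions at both visits or one cuff reading per dose, is not supported by the documents' figures, and each of these involves a trade-off.

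**Conclusion.** No change to the plan follows. The observation is accurate: Sections 1.2 and 8.3 leave the CVC scale unstated, and no section gives a rule for placing probes on the forearm. But no rule in the plan is shown to give a wrong result. The measured site maximum and its stated role tell an analyst what is intended, and every ingredient for either scale is recorded.

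The size of any effect cannot be fixed from the documents. Under the assumed SDs, gain CVs and errors, the variance ratio spans about 0.5 to 14, and the direction of the sample-size comparison depends on whether the groups differ in their maximum. The conclusion rests on the study remaining a pilot of six women whose number and final protocol are set by a later modification. The scale and placement would need to be explicit in that modification, where a confirmatory comparison would depend on them.
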